Health
Sydney
Local Health District

PMBC Sleep Program

PROTOCOL NUMBER: VERSION 1.0 (APRIL 2018)

ADMINISTRATIVE INFORMATION

DATA CATEGORY	INFORMATION
Scientific Title	A pilot evaluation of sleep program to improve sleep quality in male psychiatric HDU inpatients
Public Title	PMBC sleep program
Date of Registration	TBC
Primary registry and trial identification number	TBC
Date of Registration in primary registry	TBC
Secondary identification numbers	TBC
Source of monetary or material support	Fully funded by the Sydney Local Health District (\$50,000)
Primary Sponsor	Sydney Local Health District
Contact for public queries	[name] [name], [contact]
Contact for scientific queries	[name] [name], [contact]
Countries of recruitment	Australia
Health condition(s) or problem(s) studied	Inpatient male HDU psychiatric patients of all diagnoses
Intervention(s)	Ward-based initiatives and activity groups
Comparator	Routine male inpatient psychiatric HDU patients' length of stay with and without therapy; previous admissions
Inclusion criteria	Males aged 18+ years. Able to give informed written consent. Literacy in English. Inpatient at PMBC psychiatric Male High Dependency Unit (HDU).
Exclusion criteria	Current substance dependence. Severely unwell such that not able to give consent or tolerating participation in group sessions. Severe cognitive impairment or thought disorder. Not

	proficient in English. Recent transmeridian (>2 time zones) travel (within last 1 month).
Study type	Interventional; Allocation: nonrandomized; Masking: none (open label trial)
Primary Purpose	Pilot Study, Feasibility Study
Date of first enrolment	May 2018
Target sample size	N/A (Pilot study, rolling recruitment)
Recruitment status	Recruitment not yet commenced.
Primary outcomes	Actigraphic changes in sleep duration (Respironics Actigraphy data)
Key secondary outcomes	
Sleep quality (weekly Visual Analogue Scale (VAS) and Pittsburgh Sleep Quality Index measured at start and end of study)
 
Self-report duration
 
Length of stay in HDU
 
Use of as needed (PRN) sedatives for sleep
 
Sleep efficiency (actigraphy)
 
Engagement in group
 
Autonomy
 
Participant satisfaction

Protocol Version:	Version 1.0, April 2018
Revision Chronology	Version 1.0, April 2018: Original.
Protocol Amendment Number	0
Authors	[name] BE(Hons) BCom MBBS, [name] BPsych(Hons), [name] MBBS PhD

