In conclusion, scientific research suggests that in the clinical setting, actigraphy is reliable for evaluating sleep patterns in patients with insomnia, for studying the effect of treatments designed to improve sleep, in the diagnosis of circadian rhythm disorders (including shift work), and in evaluating sleep in individuals who are less likely to tolerate PSG, such as inpatient psychiatric patients. While actigraphy has been used in research studies for many years, it is only recently that the methodological issues have been systematically addressed in clinical research and practice. With those issues addressed, the use of actigraphy is now being applied to clinical practice. (Ancoli-Israel et al, 2003).

STUDY OBJECTIVES

Primary Objective

To evaluate the effect of the Sleep Program on duration of admission in HDU (compared to controls) and sleep duration (Actigraphy data), in male psychiatric HDU inpatient participants.

Secondary objectives

1. Sleep quality - improvement in the Pittsburgh Sleep Quality Index
2. Sleep efficiency- percentage time in bed vs percentage time asleep
3. To test the engagement (tolerability and practicality) with a structured Stimulus Control Therapy Program
4. Impact on use of as needed (PRN) hypnotics
5. To describe the characteristic of sleep, activity and light exposure of patients in a high dependency psychiatric unit using wrist actigraphy.

Hypotheses

- We hypothesise that a structured stimulus control program for sleep will shorten duration of admission at psychiatric HDU.
- There will be an improvement in the sleep duration and efficiency
- There will be an improvement in the quality of sleep via a reduction of the self-rated Pittsburgh Sleep Quality Index score, measured at the beginning and end of the study.
- Participants in the Bright Light Study will engage in a structured stimulus control therapy program and it will be well-tolerated.

STUDY DESIGN

Design, Study Groups, Number of Participants

This is a pilot study for a complex intervention and we do not know the effect of variance. We seek to test our methodology, exterminate recruitment and retention rates, feasibility and finally, determine the sample size. We also seek to highlight any issues with acceptability, compliance, and delivery of our interventions.

Number of centres

Single-centre, at [name] Centre, male High Dependency (psychiatric) Unit

Duration

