We foresee the duration of the pilot study of approximately 6 months. Recruitment is on a continuous basis; with approximately 4-6 patients recruited at any given time.

Initial recruitment phase is one week, where patients are identified (see recruitment procedures).

Initial recruitment will be 4-6 patients. The patient is recruited for as long as they are an inpatient at the HDU and discontinued at their discharge (or at their request). Subsequent patients are then recruited in the same process to maintain 4-6 patients at any given time in the program for the duration of the pilot study.

PARTICIPANTS

Inclusion Criteria

1. Males 18+ years.
2. Inpatient in psychiatric Male HDU at PMBC
3. Willingness to give informed written consent and willingness to participate to and comply with the study.
4. Literacy in English.

Exclusion Criteria

1. Current substance dependence.
2. Severe cognitive impairment or thought disorder that does not allow participants to consent or follow treatment instructions.
3. Recent time-zone travel (within last 1 month).

STUDY OUTLINE

Interventions

The intervention is an integrated Sleep Program. It comprises of two main components, thrice weekly group sessions and ward environmental initiatives. The overarching aim is to improve sleep through;

1. **Increase daytime activity**, particularly in the morning if possible, with use of the balcony and outdoor areas. It has the ultimate aim of establishing routine. Many patients in a hospital setting experience a lack of activity. For example, patients may spend a lot of time in bed watching TV or napping throughout the day.
2. **Setting regular rhythms** – enhanced light/dark exposure to stabilize circadian rhythms.
3. **Stimulus control and relaxation** – simple breathing techniques, relaxing music through headphones, relaxation on bean bags
4. Encourage patient-driven management through **psychoeducation**, ongoing sleep quality monitoring and feedback, and driving behavioural change in the ward milieu.

The total duration of a patient’s participation in the Program is flexible. However, we consider a 2-week duration as the minimum dose.

Ward environmental initiatives

A number of initiatives are adopted, these are summarised below. They are specific to the participants of the study. Bean bag and visual cues (ward posters) are made available to the participants in their own rooms; while headphones are pre-existing equipment available to all patients in the HDU.

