- familial distress
- harm to any member of a vulnerable population
- reputational harm

Informed Consent Process

There is a one-stage consent process to entry into the study. The Senior occupational therapist, [name] (investigator in this study) will introduce the study and discuss the main aspects to potential eligible participants in person in the first instance to reduce medical-patient power imbalance.

Participants will receive the study information sheets in hard copy. Research clinicians will discuss the study with participants in light of the information provided to them. The research clinician will obtain written content from patients willing to participate.

A potential participant has one week to consider their participation; however, they may defer that decision up until two weeks prior to their expected discharge date from the HDU - given a meaningful study period is defined as a minimum of two weeks of participation.

Enrolment Procedure

The participant will be enrolled into the study after the informed consent process has been completed and the participant has met all inclusion criteria and none of the exclusion criteria.

Participants need to be inpatient at HDU North (male) in PMBC, Royal Prince Alfred Hospital.

Participants are first identified as potential (candidate) participant by medical/OT/SW/RN from Multi-Disciplinary Team (MDT) meeting, satisfying inclusion and exclusion criteria.

The participant will receive a study enrolment number (Participant ID number), and this will be documented in secure and confidential register, as well as in the medical records.

Capacity

Potential (candidate) participants are clinically assessed for the ability to understand and capacity to give consent. The consultant in the treating team must deem the candidate participant as having capacity to consent; and this must be a consensus impression by the rest of the MDT. Further, it must be verifiable by demonstrated understanding and engagement with the Sleep Program. Mental state is monitored on an ongoing basis as per standard care. In cases where a participant deteriorates or loses capacity to consent and participate altogether: their involvement in the study will cease. This is outlined under *Early Terminations*.

Randomisation Procedure

Not applicable

Adverse Event Reporting

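### Clinician-controlled entry, with no offer rule and no count of eligible men, leaves the length-of-stay comparison open to selection of unknown size and direction and the recruitment rate without an eligible denominator

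*Protocol*

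**What the plan says.** - **Allocation.** The administrative table gives the study type as "Interventional; Allocation: nonrandomized; Masking: none (open label trial". The Randomisation Procedure section is marked not applicable.
- **Who proposes candidates.** Enrolment Procedure: "Participants are first identified as potential (candidate) participant by medical/OT/SW/RN from Multi-Disciplinary Team (MDT) meeting, satisfying inclusion and exclusion criteria". The Participant Time Line adds screening at handover by clinical staff and a medical assessment of appropriateness, for which no standard is given.
- **Capacity.** "The consultant in the treating team must deem the candidate participant as having capacity to consent", with agreement from the rest of the team.
- **Places.** Under Duration: "Subsequent patients are then recruited in the same process to maintain 4-6 patients at any given time in the program". No section says in what order eligible men are approached.
- **Timing.** Under Informed Consent Process, men have a week to decide, but "they may defer that decision up until two weeks prior to their expected discharge date from the HDU". Under Interventions, "we consider a 2-week duration as the minimum dose".
- **Exclusions.** The administrative table excludes men described as "Severely unwell such that not able to give consent or tolerating participation in group sessions". The Early Termination section removes men who stop early from results and statistical analyses.
- **What is compared.** The Primary Objective begins "To evaluate the effect of the Sleep Program on duration of admission in HDU (compared to controls" and then adds actigraphic sleep duration. The comparator row of the administrative table names routine HDU patients' stay with and without therapy, and previous admissions. The same table lists length of stay as a key secondary outcome.
- **Analysis.** The Statistical Analysis Plan section intends within-person differences of means and expects too few data for regression.
- **Recruitment.** Study Design makes recruitment and retention rates an aim of the pilot. The register described under Enrolment Procedure records enrolled participants.

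**The concern.** Men enter through treating staff, into few places, with no stated order of offer. If more men are eligible than there are places, someone decides who is offered one, and the staff making that decision also work with an expected discharge date. That date is a forecast of the outcome being compared. Men passed over can then fall among the routine patients without therapy. Applying the eligibility criteria to the comparator would not remove such selection, because the choice is made among eligible men. The section on analysis does not expect adjustment to be feasible.

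Two things are at stake. A difference in HDU stay could be read as an effect of the Program when it reflects who got in. The recruitment rate, which this pilot exists to estimate, would show how fast 4-6 places turn over and would not show what share of eligible men could be recruited. Men who were eligible but never approached cannot be reliably counted afterwards.

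**Working it through.** **Figures in the protocol.** It gives no sample size, target effect on stay, SD, ward size or number of eligible men, so there is no figure to reproduce. The only stay difference in days is 3.67, in the background, from a study of east- and west-facing rooms. Everything below is illustration under assumed inputs, with zero Program effect throughout.

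**1. Staff choice related to prognosis.** Let f be the share of eligible men given a place and r the correlation between staff prognosis and HDU stay. Under normal selection the gap between chosen and not-chosen men is

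gap = r × φ(z_f) × (1/f + 1/(1−f)) SD.

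At f = 0.5, φ(0) = 0.399 and the bracket is 4:

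| r | gap in SD | SD 7 days | SD 10 days | SD 14 days |
|---|---|---|---|---|
| 0.2 | 0.2 × 0.399 × 4 = 0.319 | 2.2 | 3.2 | 4.5 |
| 0.3 | 0.3 × 0.399 × 4 = 0.479 | 3.4 | 4.8 | 6.7 |
| 0.5 | 0.5 × 0.399 × 4 = 0.798 | 5.6 | 8.0 | 11.2 |

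At f = 0.25 or 0.75 the gaps are 0.339, 0.508 and 0.847 SD. Skewed stays were also simulated (1,000,000 lognormal stays, mean 14-42 days, coefficient of variation 0.6-1.0). Choosing the better-prognosis half shortened Program stays by 2.5-11.2 days at r = 0.2, 3.7-16.6 at r = 0.3 and 6.1-27.1 at r = 0.5. If staff instead favour men expected to stay longer, the sign reverses.

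**2. Two-week minimum.** In the same lognormal stays, admitting only stays of at least 14 days makes Program stays 1.4 to 13.4 days longer than all HDU stays. This runs against the Program.

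**3. Having to be present when a place opens.** I simulated a rolling ward with 5 places, 8-15 beds always full, mean stay 14-21 days and coefficient of variation 0.7. All men were eligible and consenting, and choice was unrelated to prognosis. The excess stay of enrolled over non-enrolled men was:

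| How a vacancy is filled | No minimum | 14 days of stay must remain |
|---|---|---|
| At random among those present | about 6-10 days | about 15-19 days |
| Earliest HDU admission first | about 10-18 days | about 15-24 days |

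A gap therefore remains even when staff choice has nothing to do with stay. Long stayers are more likely to be on the ward when a vacancy arises. Filling by admission date adds to this, since it favours the man who has already stayed longest.

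**4. Early terminations.** Dropping them removes men who deteriorated or were transferred, and also men who felt their sleep had improved enough. The net effect on stay may go either way.

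**5. Net.** The components run in opposite directions, each can amount to several days, and none can be estimated from the document. None of these calculations models the comparison with previous admissions.

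**6. Recruitment.** Two ratios are needed: offered/eligible and consented/offered. The second can be obtained from men approached. The first cannot, because no count of eligible men is planned.

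**The case against.** The design is openly non-randomised and unmasked, and it is a pilot. The key sentence describes screening against the eligibility criteria, with capacity assessment and the man's own consent to follow. It does not describe a choice among eligible men. The 4-6 figure reads as an approximate target and need not be a hard cap. With the exclusions, the capacity consensus and the two-week minimum, there may seldom be more eligible men than places. The registered primary outcome is actigraphic sleep duration, analysed within person.

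Much of this stands, and it rules out several stronger readings that a reader might infer:

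- *That staff hand-pick men knowing their prognosis.* The text shows clinical control of entry, no ordering rule and use of an expected discharge date. Deliberate choice on prognosis is an inference.
- *That allocation is fully predictable.* That criticism belongs to a randomised sequence. Here there is none, and the problem is confounding.
- *That the bias is as large as the effect sought.* No effect on stay is stated, and 3.67 days is background from a different question.
- *That the bias favours the Program.* Steps 2 and 3 of the working point the other way.
- *That the recruitment rate cannot be interpreted at all.* Consent among men approached remains estimable.

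Declaring non-randomised allocation discloses a limitation. It does not supply the missing count, and it does not reconcile a between-group primary objective and a hypothesis of shorter admission with a comparison that cannot carry them. Nor is this a matter to leave to an analysis plan, since the log has to be kept during enrolment.

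**Conclusion.** The point holds in limited form. Entry is clinician-controlled, about 4-6 places are refilled, and the protocol fixes neither who is offered a free place nor any count of eligible men not offered one. If eligible men exceed places, which the document does not state, the comparison of HDU stay with routine patients is confounded by selection of unknown size and direction. Presence at a vacancy and the two-week minimum lengthen Program stays; staff choice and the removal of early terminations may act either way. Differences of several days are plausible under the assumed inputs, but no single figure is defensible. The missing eligible denominator requires no assumption about bias. The within-person actigraphy result is outside this between-group argument.

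**What to change.** 1. **Enrolment Procedure.** Have the MDT list every man when he first meets the criteria. Record in the existing confidential register the date and the outcome: offered, consented, declined, or no place available. Eligibility and capacity judgements stay with the clinicians.
2. **Recruitment reporting.** Report offered/eligible and consented/offered.
3. **Primary Objective and first hypothesis.** State that the length-of-stay comparison with controls is descriptive only and will not support a conclusion that the Program shortens admission.
4. **Order of offers.** Do not offer places strictly by HDU admission date; in the simulation this raised the zero-effect gap from about 6-10 to about 10-18 days. If an order is wanted, choose by chance among the listed eligible men. That removes staff choice but not the bias from having to be present when a place opens.

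The cost is a short protocol paragraph and a few register columns, with no extra staff or patients. The downside is a weaker length-of-stay claim and, if chance ordering is adopted, less staff discretion over who is approached first. The comparison remains non-randomised, and differences arising from consent itself remain.

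### Engagement with the Sleep Program is part of the entry check, early leavers are dropped from the results, and engagement is also an outcome, so the engagement and tolerability results lean upward

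*Protocol*

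**What the plan says.** **Entry.** The Capacity section opens with "Potential (candidate) participants are clinically assessed for the ability to understand and capacity to give consent". The treating consultant must find capacity and the multidisciplinary team (MDT) must agree. The section then adds: "Further, it must be verifiable by demonstrated understanding and engagement with the Sleep Program". Enrolment Procedure places this before entry: "The participant will be enrolled into the study after the informed consent process has been completed".

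**Outcome.** The Administrative Information table lists "Engagement in group" among the key secondary outcomes. Secondary objective 3 is "To test the engagement (tolerability and practicality) with a structured Stimulus Control Therapy Program". The last hypothesis states that participants "will engage in a structured stimulus control therapy program and it will be well-tolerated". The Study Design section also names recruitment, retention, acceptability and compliance as things the pilot should learn.

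**Analysis.** Early Termination lists five circumstances:

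1. The patient's own decision, for reasons that include side-effects, intolerability and feeling that sleep has improved enough.
2. Loss of capacity.
3. No longer being able to take part.
4. Medical admission.
5. Transfer to another facility.

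Data from these men are set apart from the main pool. They are kept for discussion only and left out of both the results and the statistics.

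**The concern.** A pilot of a ward program has to learn whether patients take part in it and can bear it. That result is informative only if men who do not engage, or who find the Program intolerable, can appear in it. Here one rule lets engagement count towards admission, and another removes several groups for whom the Program went badly. Both act on the quantity being measured. A full trial planned from the surviving figure could overestimate attendance and underestimate dropout. A statistical analysis plan could define the engagement measure. It could not recover data on men who were never admitted, and the exclusion of early terminations is already fixed in the protocol.

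**Working it through.** The protocol states no engagement rate, number approached or number expected to terminate, so there is no figure to reproduce. The check compares the rules and then works out the direction of bias.

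**Step 1: the rules side by side**

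| Stage | Protocol section | Effect on engagement or tolerability |
|---|---|---|
| Before entry | Capacity | Engagement with the Program is part of verifying capacity |
| Measured | Administrative Information; Secondary objectives, item 3; Hypotheses | Engagement and tolerability are the result |
| Analysis | Early Termination | Stops for side-effects, intolerability or inability to take part are removed |

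No section separates the engagement used to verify capacity from the engagement measured as an outcome.

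**Step 2: the two readings of the capacity sentence**

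- *As an entry check.* This is the literal reading, since the paragraph is about candidates. Engagement is then partly selected for. There is also a problem of order. The Participant Time Line starts the groups at recruitment, not at screening, and the Summary table of sessions places consent inside Session 1. Engagement with the Program would be needed to verify a consent that precedes it.
- *As continuing verification after entry.* Poor engagement could then be read as evidence that capacity has been lost. Under the Capacity section loss of capacity ends involvement, and under Early Termination the data leave the results. The outcome is still conditioned partly on itself, at a later point.

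**Step 3: direction of the bias**

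Treat engagement as yes or no. All three inputs are assumptions:

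- *p*: true share of candidates who would engage
- *q*: share of non-engagers removed by either rule
- *r*: share of engagers removed by either rule

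Observed engagement = p(1 − r) / [p(1 − r) + (1 − p)(1 − q)].

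This exceeds p whenever q > r. The capacity sentence points that way, as do terminations for intolerability or inability to take part. Transfer, medical admission and leaving because sleep has improved have no clear direction.

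**Step 4: illustration with r = 0**

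The formula reduces to p / [p + (1 − p)(1 − q)].

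| p | q = 0 | q = 0.5 | q = 1 |
|---|---|---|---|
| 0.40 | 40% | 0.40 / (0.40 + 0.30) = 57% | 100% |
| 0.60 | 60% | 0.60 / (0.60 + 0.20) = 75% | 100% |
| 0.80 | 80% | 0.80 / (0.80 + 0.10) = 89% | 100% |

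The q = 1 column is the limit in which every non-engager is removed. Nothing in the protocol says the rules would work so completely. The table shows direction and sensitivity and is not an estimate for this trial.

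**The case against.** The strongest reply is that the outcome is far from settled in advance. The capacity sentence sets no threshold. Participants are invited to sessions and not obliged to attend, and the Friday evening session is optional. Program usage is recorded at recruitment, weekly and at discharge. Adverse events are checked at each session, and a satisfaction survey is given. A man who engages at entry may later attend little or report discomfort. This stands. A reader might infer that the hypothesis cannot fail or that the plan would report 100% engagement; the text does not support either.

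A reader might also infer that everyone who stops engaging is dropped. That is not what Early Termination says. Non-attendance is not a listed circumstance, and termination runs through notice to an investigator and then to the Study Coordinator. A man who simply stops coming remains in the data.

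Two other criteria may seem to add to the problem: "willingness to participate to and comply with the study" in the Inclusion Criteria, and "Severely unwell such that not able to give consent or tolerating participation in group sessions" in the Administrative Information table. Both are ordinary suitability conditions for a group intervention and are not circular in themselves.

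Planned exposure before consent is likewise only an inference. The sentence may mean engagement with the Program as presented during the consent discussion, and the Friday breakfast is open to the whole ward anyway. If the consent discussion was meant, the wording should say so.

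Finally, a rate over men named at the MDT meeting would not be the share of all HDU patients who would use the Program. Those men have already been screened against the criteria, and they may fail to enter for reasons unrelated to engagement. This also stands and shapes the fix.

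None of these replies removes the exclusion of men who stop for side-effects, intolerability or inability to take part, or separates the entry check from the outcome.

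**Conclusion.** The concern holds as a matter of bias. Selection at entry and exclusion at analysis both favour the engagement and tolerability hypothesis. A graded measure can still vary among those admitted, so the result is tilted upward and not predetermined. The conclusion rests on two assumptions: that the capacity sentence is applied as written, and that the two rules together remove poor engagers more often than good ones. The size cannot be computed from the documents. It depends on how strictly the entry check is used and on how many men terminate, and for what reason. The point affects a key secondary outcome and the pilot's feasibility aims. It should be corrected before enrolment because the remedy is simple and men lost at entry leave no data to repair the result later.

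**What to change.** 1. **Early Termination.** State that the exclusion does not apply to engagement, tolerability or retention. Report these over all consented participants, including early terminations, with the reason for each. A workable engagement measure is sessions attended divided by sessions offered while enrolled.
2. **Capacity.** Reconcile the sentence with the consent sequence so that engagement with the Program is not both a condition of entry and an outcome. One way is to refer to understanding of the study information and the consent discussion. The clinical assessment of capacity by the consultant and the MDT stays as it is.
3. **Recruitment.** Report how many candidates identified at the MDT meeting did not enter, with reasons, as a recruitment figure and not as an engagement rate.

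The cost is a few sentences in the protocol and a simple tally at a meeting that already takes place. Early-termination data are already to be kept, and Program usage is already scheduled for recording. The downside is that the reported engagement rate will probably be lower.
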